### 5.1.3 Crude incidence and related risk estimates

#### 5.1.3.1 Crude incidence and $100*(1-\alpha)$ % confidence interval

For  $n$  subjects, each at risk to experience a certain event with probability  $\pi$ , the crude incidence is estimated as  $p=x/n$ , where  $x$  is the number of subjects with the event.

Absolute and relative frequencies will be displayed as well as 95% confidence interval for the relative frequency based on the score method including continuity correction ([Newcombe 1998](#)).

With  $z$  as  $(1-\alpha/2)$ -quantile of the standard normal distribution (SAS:  $z=PROBIT(1-\alpha/2)$ ),  $n$  as total number of subjects (i.e. number of subjects in the denominator), and  $p$  as estimated crude incidence (number of subjects with event /  $n$ ) it is  $q = 1 - p$ .

Then the lower limit is

$$L = \max \left( 0, \frac{2np + z^2 - 1 - z\sqrt{z^2 - 2 - \frac{1}{n} + 4p(nq+1)}}{2(n+z^2)} \right)$$

and the upper limit is

$$U = \min \left( 1, \frac{2np + z^2 + 1 + z\sqrt{z^2 + 2 - \frac{1}{n} + 4p(nq-1)}}{2(n+z^2)} \right).$$

Note: if  $p = 0$  then  $L = 0$  and if  $p = 1$  then  $U = 1$ .

If appropriate, an exact  $100*(1-\alpha)\%$  confidence interval ([Clopper-Pearson 1934](#)) will be obtained by using the SAS procedure PROC FREQ with the EXACT BINOMIAL statement. However, the confidence interval derived via the score method including continuity correction will be the default in safety analyses.

### 5.1.3.2 Relative risk and 100\*(1- $\alpha$ )% confidence interval

For an investigational drug group with  $n_1$  subjects at risk, independent from the control group (e.g., placebo or comparator) with  $n_0$  subjects at risk, of whom  $x_1$  and  $x_0$  experience a certain event with probability  $\pi_1$  and  $\pi_0$  respectively, the relative risk is estimated as  $p_1/p_0$  with  $p_1=x_1/n_1$  and  $p_0=x_0/n_0$ .

An asymptotic 100\*(1- $\alpha$ )% confidence interval on the relative risk will be based on the back-transformed large sample confidence limits on the log-transformed relative risk estimate which are obtained by application of the delta-method and Slutsky's theorem (Lachin 2000). The SAS procedure PROC FREQ with option RELRISK in the TABLES statement will be used to provide the asymptotic 100\*(1- $\alpha$ )% confidence interval on the relative risk. The estimate is not computed if either  $x_1$  or  $x_0$  equals 0. In this case, or if the crude incidences are low in both groups, the relative risk will be approximated by the odds ratio for which an exact confidence interval will be obtained. If the relative risk is not well approximated by the odds ratio but asymptotic normality is questionable, STATXACT will be used.

### 5.1.3.3 Odds ratio and 100\*(1- $\alpha$ )% confidence interval

For an investigational drug group with  $n_1$  subjects at risk, independent from the control group (e.g. placebo) with  $n_0$  subjects at risk, of whom  $x_1$  and  $x_0$  experience a certain event with probability  $\pi_1$  and  $\pi_0$  respectively, the odds ratio is estimated as

$$\frac{p_1/(1-p_1)}{p_0/(1-p_0)}$$
 with  $p_1=x_1/n_1$  and  $p_0=x_0/n_0$ . A conditional exact 100\*(1- $\alpha$ )% confidence interval will be obtained by using the SAS procedure PROC FREQ with statement EXACT OR.

### 5.1.3.4 Risk difference and 100\*(1- $\alpha$ )% confidence interval

For an investigational drug group with  $n_1$  subjects at risk, independent from the control group (e.g., placebo or comparator) with  $n_0$  subjects at risk, of whom  $x_1$  and  $x_0$  experience a certain event, the risk difference is estimated as  $p_1-p_0$  with  $p_1=x_1/n_1$  and  $p_0=x_0/n_0$ .

Exact unconditional confidence limits for the risk difference will be obtained with SAS procedure PROC FREQ and option RISKDIFF in the TABLES statement, specifying the RISKDIFF option also in the EXACT statement.

## 5.1.4 Exposure adjusted incidence rate and related risk estimates

### 5.1.4.1 Exposure adjusted incidence rate and 100\*(1- $\alpha$ )% confidence interval

[figure not shown]
It will be assumed that for each of  $n$  subjects in a clinical trial the time  $t_j$  ( $j=1, \dots, n$ ) to the first occurrence of a certain treatment emergent event is observed, or if the event was not experienced, the (censored) time to the end of the observation period or last dose plus 84 days whichever occur earlier. The sequence of first occurrences of an event will be modelled to follow approximately a Poisson process with constant intensity  $\theta$ . The rate parameter  $\theta$  will be estimated as  $\lambda=D/T$ , where  $T = \sum_{j=1}^n t_j$  and  $D$  is the number of subjects

with at least one event. Conditionally on T, an exact  $100*(1-\alpha)\%$  confidence interval for a Poisson variable with parameter  $\theta T$  and observed value D can be obtained based on [Garwood, 1936](#), from which an exact  $100*(1-\alpha)\%$  confidence interval for D/T will be derived as follows ([Sahai, 1993](#); [Ulm, 1990](#)):

$$\text{Lower confidence limit } L = \frac{0.5c_{\alpha/2,2D}}{T} \text{ for } D>0, 0 \text{ otherwise,}$$

$$\text{Upper confidence limit } U = \frac{0.5c_{1-\alpha/2,2D+2}}{T}$$

where  $c_{\alpha k}$  is the  $\alpha$ th quantile of the Chi-square distribution with k degrees of freedom.

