### 7.2.2 SAE reporting

To ensure patient safety, every SAE, regardless of causality, occurring after the patient has provided informed consent and until 20 weeks after last dose was taken or until 30 days after

the last study visit (whichever is later) must be reported to Novartis within 24 hours of learning of its occurrence. Any SAE reported until 20 weeks after last dose was taken or until End of study visit (whichever is later) must be recorded in the AE eCRF. SAEs beyond that date will only be recorded in the Novartis Drug Safety and Epidemiology database.

Any SAEs experienced after the 30 days from end of study visit or after the 20 weeks since last dose was taken (whichever is later), should only be reported to Novartis if the investigator suspects a causal relationship to study treatment.

Recurrent episodes, complications, or progression of the initial SAE must be reported as follow-up to the original episode, regardless of when the event occurs. This report must be submitted within 24 hours of the investigator receiving the follow-up information. An SAE that is considered completely unrelated to a previously reported one should be reported separately as a new event.

Information about all SAEs (either initial or follow up information) is collected and recorded in English on the paper Serious Adverse Event Report Form or the electronic Serious Adverse Event Form within the Oracle Clinical/Remote Data Capture (OC/RDC) system (where available). The Investigator must assess the relationship to each specific component of the study treatment (if the study treatment consists of several components).

SAEs (initial and follow-up) that are recorded *on the paper SAE form* should be faxed within 24 hours of awareness of the SAE to the local Novartis Drug Safety and Epidemiology Department. The telephone and fax number of the contact persons in the local department of Drug Safety and Epidemiology, specific to the site, are listed in the investigator folder provided to each site. The original copy of the SAE Report Form and the fax confirmation sheet must be kept with the case report form documentation at the study site. Follow-up information should be provided using a new paper SAE Report Form stating that this is a follow-up to a previously reported SAE

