### 1.1 Study design

This is a multicenter, randomized, double-blind, placebo-and active-controlled (etanercept in single blinded arm) study in pediatric subjects aged 6 years to less than 18 years with severe chronic plaque psoriasis. Approximately 160 subjects aged 6 years to <18 years will be enrolled, of which at least 30 pediatric subjects will be 6 years to <12 years old. In reality around 40-45 patients will be needed to meet the requirement of recruiting about 30% of subjects in the < 25kg weight group.

Subjects will be randomized using a 1:1:1:1 ratio into one of the treatment arms: secukinumab low dose, secukinumab high dose, etanercept or placebo. The randomization will be stratified by age (<12 years or ≥12 years) and weight (<25 kg, 25-<50 kg, ≥50kg) at randomization. Subjects randomized to the placebo group will be pre-assigned to either the low- or high-dose group of secukinumab, at the Randomization visit, in case they are not achieving a PASI 75 response as assessed at Week 12.

The study consists of 5 Epochs: screening (up to 4 weeks), induction (of 12 weeks), maintenance (of 40 weeks), extension treatment epoch (open-label of 184 weeks) and post-treatment follow-up epoch (of 16 weeks). The detailed information of the study design is described in [Figure 1-1](#).

**Figure 1-1** Study design

The following study periods will be considered for analysis:

- **Screening period** (before Randomization)
- **Induction period** (Randomization to Week 12 pre-dose), including follow-up period (F4, F8, F12 and F16 (EOF) visits) for prematurely discontinued subjects before Week 12 completion. For placebo PASI 75 responders at Week 12, subjects will enter follow-up period after Week 12, including the first visit F4 and four weeks later visit EOF at F8.
- **Maintenance period** (Week 12 dose to Week 52 pre-dose), including follow-up period (F4, F8, F12 and F16 visits) for prematurely discontinued subjects before Week 52 completion, and for etanercept patients with the completion of the maintenance epoch.
- **Extension period** (Week 52 dose until Week 236 (EOT)), including follow-up period (F4, F8, F12 and F16 visits) for prematurely discontinued subjects before Week 236 completion.
- **Entire treatment period** (Randomization to Week 236 (EOT)), for safety analysis, exposure including follow-up period up to last dose + 84 days.
- **Entire study period** (Randomization to end of study (EOS)), including follow-up period (F4, F8, F12 and F16 visits).

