#### **2.9.1 Adverse events (AEs)**

For adverse events and other binary safety variables, crude incidence and exposure time-adjusted incidence will be derived as described below and summarized in [Table 2-11](#).

Only treatment emergent adverse events will be summarized. However all AEs will be included in the listing with flags for treatment emergent. If needed a separate AE listing can be provided to display exclusively AEs with start date later than 84 days since last dose and until EOS.

Treatment emergent adverse events are defined as events started on or after the first dose of study medication or events present prior to the first dose of study medication but increased in severity after dosing based on preferred term and within last dose + 84 days.

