**Exposure adjusted incidence rates will be also provided for the entire treatment period, by the following subgroups:**

- Treatment emergent AEs by SOC, PT and by age strata
- Treatment emergent AEs by SOC, PT and by body weight strata
- Treatment emergent SAEs by SOC, PT and by age strata
- Treatment emergent SAEs by SOC, PT and by body weight strata
- Important identified and potential risks (level 1) based on all adverse events by age strata
- Important identified and potential risks (level 1) based on all adverse events by body weight strata

The crude incidence of treatment emergent adverse events will be summarized by primary system organ class and preferred term. Confidence intervals for the crude rate will be derived as described in [Section 5.1](#). In addition, exposure time-adjusted rates (incidence rate) including 95% confidence intervals may be provided.

AEs and serious AEs will be summarized by presenting, for each treatment group (including any AIN457), the number and percentage of subjects having any AE, having an AE in each primary system organ class and having each individual AE (preferred term). Summaries (crude incidences only) will also be presented for AEs by severity. If a particular AE 'severity' is missing, then this variable will be listed as missing and treated as missing in summaries. If a subject reported more than one adverse event with the same preferred term, then the adverse event with the greatest severity will be presented. If a subject reported more than one adverse event within the same primary system organ class, then the subject will be counted only once with the greatest severity at the system organ class level, where applicable.

AEs and SAEs will be presented in terms of exposure time-adjusted incidence rates with 95% confidence intervals for entire study period (up to EOS).

Adverse events will also be summarized by standardized or customized MedDRA queries (SMQ or CMQ/NMQ). The MedDRA version used for reporting the adverse events will be described in a footnote.

The most common adverse events reported ( $\geq z\%$  in any group for each preferred term in the table by SOC and PT or  $\geq z\%$  in any group for each grouping term table) will be presented in descending frequency according to its incidence in secukinumab group starting from the most common event. Here, the threshold value  $z$  is set to 4 (%) but it may be updated following review of the dry run outputs.

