### 5.2.2 AE date imputation

Impute AE end date:

1. If the AE end date 'month' is missing, then the imputed end date should be set to the earliest of the (min (last visit date, last dose date + 84 days), 31DECYYYY, date of death).
2. If the AE end date 'day' is missing, then the imputed end date should be set to the earliest of the (min (last visit date, last dose date + 84 days), last day of the month, date of death).
3. If AE 'year' is missing or AE is ongoing, then the end date will not be imputed.

Impute AE start date. Before imputing AE start date, find the AE start reference date.

1. If the (imputed) AE end date is complete and the (imputed) AE end date < treatment start date, then AE start reference date = min(informed consent date, earliest visit date).
2. Else AE start reference date = treatment start date.

If the AE start date 'year' value is missing, then the date uncertainty is too high to impute a rational date. Therefore, if the AE year value is missing, then the imputed AE start date is set to NULL.

If the AE start date 'year' value is less than the treatment start date year value, then the AE started before treatment. Therefore:

1. If AE 'month' is missing, then the imputed AE start date is set to the mid-year point (01JulYYYY).
2. Else if AE 'month' is not missing, then the imputed AE start date is set to the mid-month point (15MONYYYY).

If the AE start date year value is greater than the treatment start date year value, then the AE started after treatment. Therefore:

1. If the AE month is missing, then the imputed AE start date is set to the year start point (01JanYYYY).
2. Else if the AE month is not missing, then the imputed AE start date is set to the later of (month start point (01MONYYYY), AE start reference date + 1 day).

If the AE start date year value is equal to the treatment start date year value:

1. And the AE month is missing the imputed AE start date is set to the AE reference start date + 1 day.
2. Else if the AE month is less than the treatment start month, then the imputed AE start date is set to the mid-month point (15MONYYYY).
3. Else if the AE month is equal to the treatment start date month or greater than the treatment start date month, then the imputed AE start date is set to the later of (month start point (01MONYYYY), AE start reference date + 1 day).

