If complete (imputed) AE end date is available and the imputed AE start date is greater than the (imputed) AE end date, then imputed AE start date should be set to the (imputed) AE end date.

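### The promised entire-study AE rates have no event or censoring rule that reaches end of study, and the same 84-day cap can override a recorded AE month

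*SAP*

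**What the plan says.** SAP 1.1 defines two overlapping periods. The entire treatment period is "for safety analysis, exposure including follow-up period up to last dose + 84 days". The entire study period runs from randomization to end of study and includes visits F4 to F16.

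SAP 2.9.1 makes a firm commitment for the longer period: "AEs and SAEs will be presented in terms of exposure time-adjusted incidence rates with 95% confidence intervals for entire study period (up to EOS"). The Entire study row of Table 2-11 lists the same rates for AEs, SAEs and important risks.

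Only one exposure-adjusted rate is defined, in SAP 5.1.4.1. It uses the time "to the first occurrence of a certain treatment emergent event is observed" or, without an event, "the (censored) time to the end of the observation period or last dose plus 84 days whichever occur earlier". SAP 2.9.1 also states: "Only treatment emergent adverse events will be summarized". SAP 2.9 mentions an extended analysis of AE records up to EOS, but only as something that may be provided.

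The late data are collected on purpose. Protocol 7.2.2 requires reporting of every SAE "occurring after the patient has provided informed consent and until 20 weeks after last dose was taken", or for longer if the last visit is later.

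For AE dates, SAP 5.2.2 imputes an end date with a missing day as the "earliest of the (min (last visit date, last dose date + 84 days), last day of the month, date of death"). It then adds that if "the imputed AE start date is greater than the (imputed) AE end date, then imputed AE start date should be set to" the end date.

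**The concern.** For anyone followed beyond 84 days after last dose, the 5.1.4.1 minimum is always last dose plus 84 days. Treatment-emergent events stop at the same point. Numerator and person-time for the entire study are then those of the entire treatment period, so the row meant to cover off-treatment follow-up adds nothing.

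A programmer could instead follow the remark in 2.9 and count AEs up to EOS. Without a matching person-time rule, the late events would be divided by time that stops at day 84. Both routes follow from the text, and neither gives the rate that was promised.

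The date rules have a separate defect. A cap suited to on-treatment exposure is applied to the calendar date of an AE, even when the recorded month shows that the AE happened later. In this long paediatric safety study, what is at stake is how post-treatment events are reported.

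**Working it through.** **Timing: reproduce the plan's figure first.** Protocol 3.1 (Follow-up Epoch) puts F8 at 12 weeks after the last secukinumab dose. The last dose is Week 232, Day 1625 (Protocol 5.2 and Table 6-2). 1625 + 84 = Day 1709, which is the scheduled F8 day. F16 is Day 1765, which is last dose + 140 days.

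**Follow-up cut by the cap.**

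| Group | Last dose | Last dose + 84 | Last follow-up visit | Days cut |
|---|---|---|---|---|
| Secukinumab completer | Day 1625 | Day 1709 | Day 1765 | 56 |
| Etanercept completer (Week 51) | Day 358 | Day 442 | Day 365 + 112 = 477 | 35 |
| Placebo PASI 75 responder (Week 8) | Day 57 | Day 141 | Week 20 = Day 141 | 0 |
| Early discontinuer, last dose Week 8 | Day 57 | Day 141 | 57 + 28 + 112 = Day 197 | 56 |

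- Share of person-time for an event-free secukinumab completer: 56/1765 = 3.2%. For an assumed 80 such subjects, 374.3 patient-years become 386.6 with censoring at EOS (+12.3).
- Share for the Week 8 discontinuer: 56/197 = 28%.
- Trial total, taking 40 per arm, all placebo subjects switching to secukinumab, etanercept dosed through Week 51, and everyone event-free and fully followed: (120 × 56 + 40 × 35)/365.25 = 22.2 patient-years.

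**Effect on the rate.** The rate is D/T. D is the number of subjects with an event, and T is time to first event or censoring. The simulation assumed 80 secukinumab completers and a true rate of 5 per 100 patient-years up to day 84 after last dose. The rate after that was 1, 2 or 3 times as high. Entries are mean rates per 100 patient-years.

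| Rate after day 84 | Entire treatment | Entire study, 5.1.4.1 literally | AEs to EOS, person-time capped | AEs and person-time to EOS |
|---|---|---|---|---|
| ×1 | 5.040 | 5.040 | 5.190 | 5.046 |
| ×2 | 5.062 | 5.062 | 5.346 | 5.198 |
| ×3 | 5.035 | 5.035 | 5.463 | 5.314 |

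The literal reading repeats the entire-treatment rate whatever happens after day 84. The mixed reading is too high: 5.190/5.046 = 1.03.

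**Dates.** Illustrative subject: first dose 1 Mar 2016, last dose 11 Aug 2020, cap 3 Nov 2020, last visit 29 Dec 2020, and an AE recorded in Dec 2020. With the day missing on both dates:

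1. End = earliest of (29 Dec, 3 Nov, 31 Dec) = 3 Nov.
2. Start year is after the first-dose year, so start = later of (1 Dec 2020, first dose + 1 day) = 1 Dec.
3. Start is after end, so start is reset to 3 Nov. The AE becomes treatment-emergent, although it began at least 28 days after the window closed.

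| Start recorded | End recorded | Start used | End used | Treatment-emergent? |
|---|---|---|---|---|
| Dec 2020 | Dec 2020 | 3 Nov | 3 Nov | Yes (wrong) |
| Dec 2020 | 2020 only | 3 Nov | 3 Nov | Yes (wrong) |
| Dec 2020 | 20 Dec 2020 | 1 Dec | 20 Dec | No |
| Dec 2020 | ongoing | 1 Dec | none | No |
| 5 Dec 2020 | Dec 2020 | 5 Dec | 3 Nov | No, but end precedes start |

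**The case against.** The strongest reply is that 5.1.4.1 is a general appendix formula written for treatment-emergent events. The more specific text (the period definition in 1.1, the commitment in 2.9.1 and the remark in 2.9) shows that follow-up to EOS was intended. That stands as evidence of intent, so a reader should not infer that identical rates are certain. It does not supply a rule, because no alternative numerator or censoring time is written down, and following the intent for events alone produces the mismatch shown above.

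A reader might also infer that late AEs disappear. They do not: SAP 2.9.1 lists all AEs with a treatment-emergent flag and allows a separate listing of those starting more than 84 days after last dose, and 2.9.2 commits to a summary and listing of deaths. What is missing is the committed rate with its confidence interval.

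On dates, it is fair to say that pulling a late AE into the window adds an on-treatment event, which is conservative for safety, and that few AEs will qualify. Both points stand, but the result still contradicts the recorded month.

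Finally, Protocol 9.5.3 itself sets the 84-day window for AE summaries, and the entire-study rate is a SAP addition. That supports keeping the window for the treatment period. It does not excuse an entire-study row that cannot extend past it.

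**Conclusion.** The concern holds, at modest size. The SAP commits to entire-study rates but gives no coherent way to compute them, and its AE date rules produce wrong dates in identifiable patterns.

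Two larger size claims are tempting. One is that 40% of the data is lost, from 56 of 140 post-dose days. That share describes off-treatment follow-up only; a secukinumab completer loses about 3% of the rate's person-time. The other is 160 × 56/365.25 = 24.5 patient-years. That applies the secukinumab gap to every subject, whereas etanercept completers lose 35 days and placebo PASI 75 responders none. About 22 patient-years is the most to expect if the etanercept arm is dosed through Week 51. An etanercept subject who stops earlier would lose 56 days on the protocol's schedule. Earlier first events, dropout, or leaving follow-up for another systemic treatment reduce the total.

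Nor are all partly dated late AEs moved. The pull-back needs start and end both partial, a known start month lying wholly after the window, a known end year, and an AE that is not ongoing. The documents do not say how many there are.

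The 3% upward bias rests on the assumed 80 completers and the assumed rate of 5 per 100 patient-years. The Week 12 tests, the power and the treatment-emergent definition are unaffected.

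**What to change.** 1. **SAP 5.1.4.1, Entire study row only.** Count the first AE through EOS that either starts on or after first dose, or was present before first dose and increased in severity after dosing. Censor event-free subjects at EOS. Keep last dose + 84 days for the Entire treatment row. The second limb keeps worsening pre-existing AEs in line with the definition in 2.9.1.
2. **SAP 5.2.2.** Cap a partial AE end date at the earliest of last visit, end of the recorded month (31 December if the month is missing) and death, without the 84-day term. Never set it before the first day of the recorded month or before a complete start date. In the example with both days missing, the end becomes 29 Dec and the start stays 1 Dec, so the AE is not treatment-emergent.

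The cost is a few lines of SAP text and a small programming change, with no new data. Entire-study rates will then differ slightly from entire-treatment rates, as intended.
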